6.1. INVESTIGATIONAL PRODUCT IDENTIFICATION AND USE

6.1.1. Product identity

	Investigational Product
Trade Name	Epiduo [®] Forte
Name of Active Ingredient	Adapalene - Benzoyl Peroxide
Pharmaceutical Form	Gel
Dose or Concentration	Adapalene 0.3% - BPO 2.5%
Formula number	534.0201
Total Daily dose	Four pea-sized amounts to cover whole face (e.g. one on the forehead, chin and each cheek)
Mode and frequency of administration	Topical, once daily in the evening
Location of treated area	Face
Manufacturer (Name and address)	Galderma Production Inc. (GPI) [name]
Packaging type and size (primary)	45g airless bottles with polypropylene pump system
Storage Conditions	Store at controlled room temperature 20°C to 25°C (68 °F to 77 °F). Excursions permitted be-tween 15 and 30°C (59°F et 86°F),

	Investigational Product
Trade Name	TactuPump [™] Forte
Name of Active Ingredient	Adapalene - Benzoyl Peroxide
Pharmaceutical Form	Gel
Dose or Concentration	Adapalene 0.3% - BPO 2.5%
Formula number	534.0201
Total Daily dose	Four pea-sized amounts to cover whole face (e.g. one on the forehead, chin and each cheek)
Mode and frequency of administration	Topical, once daily in the evening
Location of treated area	Face
Manufacturer (Name and address)	Galderma Production Inc. (GPI) [name]
Packaging type and size (primary)	70g airless bottles with polypropylene pump system
Storage Conditions	Store at controlled room temperature 15°C to 25°C

6.1.2. Method of treatment assignment

This will be an open label trial and all subjects will be dispensed with the investigational product. The kit number, a unique number will be assigned to each eligible subject at baseline according to the Inclusion/Non-inclusion criteria.

A subject kit will be composed of:

- Two visit boxes: One visit box will be dispensed to the subjects at Baseline (Dispensation 1) and one at week 8 visit (Dispensation 2),

One extra box to be dispensed in case if subjects loose or destroy trial treatment.

Each box will contain:

- Dispensation 1 (Baseline):

- Two Epiduo[®] Forte / TactuPump[™] Forte gel bottles

- Dispensation 2 (Week 8):

- Two Epiduo[®] Forte / TactuPump[™] Forte gel bottles

- Extra box:

- One Epiduo[®] Forte / TactuPump[™] Forte gel bottle

At baseline visit, all eligible subjects will be dispensed a Baseline visit box from the subject kit in a chronological order of inclusion into the clinical trial, without omitting or skipping any number. If a number is omitted by mistake, the skipped kit number should be allocated to the next subject.

6.1.3. IVR/IWR System

Once a Subject has fulfilled inclusion/exclusion criteria and is qualified to enter into the trial, the site will call/connect to the IVR/IWR System to check trial inclusion rate as per ethnic/race background and acne severity stratifications and assign the Subject kit number. The IVR/IWR System acts as an automatic central recruitment center.

The IVR/IWR System requires at least the Subject identification number (SIN) and Site number to provide proper treatment assignment number by linking the SIN to ethnic/race backgrounds and acne severity of the included subjects in the eCRF.

6.1.4. Subject Identification Number (SIN)

Upon signature of the informed consent, a subject meeting all inclusion/exclusion criteria will be allocated a unique subject identification number (SIN). This SIN number will be automatically generated by the eCRF.

During the whole clinical trial, the subject will only be identified using the SIN for all documentation and discussion.

6.1.5. Instructions for use and administration

The Product Dispenser will give each subject verbal and written instructions on how to use the investigational product and non-investigational products. A specific focus on risks in case of pregnancy will be made for female subjects.

In addition, at the baseline visit the Product Dispenser will show the subject how to apply the investigational product on the face and how to record these applications in the subject diary. This procedure will be thoroughly discussed and reviewed at each trial visit.

All subjects will apply the investigational product in the evening after washing their face, for 16 weeks, as described in the instructions for use provided to the subjects. The procedure is as follows:

1. Wash hands,
2. Wash the entire face using the provided Cetaphil® DermaControl™ Oil Control Foam Wash,
3. Blot dry the face with a soft towel. Do not rub the face,
4. Apply a thin film of gel on the whole face avoiding eyes, lips and mucous membranes.
DO NOT SPOT APPLY. Four pea-sized amounts should be enough to cover the whole face (e.g. one on the forehead, chin and each cheek),
5. Wash hands,
6. Complete the given subject Diary after each product application.

	Investigational Product
Concentration	Adapalene 0.3% - BPO 2.5%
Dose regimen	Once daily
Period of administration	Evening
Route of administration	Topical

6.1.6. Non-investigational products

Cetaphil® DermaControl™ Oil Control Foam Wash and Cetaphil® DermaControl™ Oil Control Moisturizer SPF 30 and Urine Pregnancy Tests (UPT) will be provided by the sponsor (or designee).

Subjects should use the provided Cetaphil® DermaControl™ Oil Control Foam Wash twice daily (once in the morning and once in the evening) in order to gently wash their face. Face should thereafter be blotted dry with a soft towel.

Subjects should use Cetaphil® DermaControl™ Oil Control Moisturizer SPF 30 once daily in the morning after washing their face, and they may use it as needed during the day (in case of sun exposure for instance).

Both products are topical and will be used on the whole face for 16 weeks.

No specific labels will be used. Subjects will not return these products to the site. No accountability will be conducted on these products.

6.2. INVESTIGATIONAL PRODUCT PACKAGING AND LABELLING

All investigational products will be supplied in the subject's kit containing 2 visit boxes (one per dispensing visit) plus an extra box.

The subject kit label will be comprised of a single panel fixed label, while the visit box labels will be comprised of a double-panel label with an affixed and a tear-off portion for accountability.

The labels will be printed in the local language. The text of the label will detail the information requested by Good Manufacturing Practice and Good Clinical Practice and local regulations. For treatment documentation, the affixed portion of the label will remain on the appropriate packaging. The tear-off portion of the label will be removed at the time of dispensation and attached to the corresponding product Dispensation Log.

6.3. INVESTIGATIONAL PRODUCT MANAGEMENT

6.3.1. Accountability

Upon receipt of the clinical supplies at the site, the investigational product Dispenser will conduct a complete inventory of all investigational products and assume responsibility for their storage, accountability and dispensation.

The Investigator or designee will sign the original “Receipt of Clinical Supplies” Form (or any acknowledgment of receipt) upon receipt and inspection of the supplies, fax the signed copy to *GALDERMA R&D* and retain the receipt in the Investigator Site File (ISF).

All supplies sent to the investigator site will be accounted for and in no case used in any unauthorized situation.

All used and unused investigational product will be appropriately inventoried by *GALDERMA R&D /CRO* representative and returned to *GALDERMA R&D* /designated contractor for further reconciliation and destruction.

6.3.2. Dispensing

All investigational and non-investigational products will be provided only to subjects enrolled into the clinical trial, at no cost and in accordance with the conditions specified in the protocol.

Dispensation will be appropriately documented on the Product Dispensation Log by the Product Dispenser at each visit.

It is important that no subject runs out of clinical trial supplies between visits. Each subject will receive a new visit box containing two bottles of investigational product at baseline and at post-baseline visit week 8.

Treatment kits will be dispensed in ascending sequential order according to the chronological order of enrolment of subjects into the clinical trial.

6.3.3. Investigational product compliance management and record

Each subject will be instructed by the Product Dispenser about the importance of being compliant with clinical trial treatment(s) throughout the clinical trial as well as the importance of returning their investigational product (used and/or not used) at week 8 and week 16 (or at the end of the trial in case of early termination) visits.

The investigational products will be collected, counted and documented on the Product Dispensation Log or other accountability document as applicable, at post-baseline visits (week 8 and week 16), by the Product Dispenser.

In this trial product compliance will be assessed using a subject diary.

At Baseline visit, subjects will be provided with a subject diary to record on a daily basis the frequency of applications of investigational product (Epiduo[®] Forte / Tactupump[™] Forte gel) and non-investigational products on the face and to record their compliance with the instructed application procedures. Subjects should return the diary at each post-baseline visit for review by the Product Dispenser. At the end of the trial week 16/early termination subjects should return the diary.

The return of investigational products should be appropriately documented on the Product Dispensation Log by the trial Product Dispenser. All subject kits will be collected at the week 16 visit at the latest, if not done before, or at Early Termination.

Subjects will also be questioned regarding the application technique, intake, frequency and missed doses of investigational product and the use of any other additional topical, systemic product as well as OTC product.

During the data review meeting, investigational product compliance for all subjects will be determined and reviewed by the sponsor's clinical team.

6.3.4. Storage of investigational product

The investigator has to agree to keep all investigational products in a safe, temperature controlled and secure area with restricted access, in accordance with applicable regulatory requirements (e.g., in the site pharmacy, if applicable).

Investigational products should be stored at appropriate storage conditions specified by *GALDERMA R&D* (see section 6.1.1).

6.3.5. Return of investigational product

The Product Dispenser will inform each subject about the importance of returning their investigational products (used and/or not used) at week 8 and week 16 at the latest, if not done before, or at Early Termination.

In the event of early termination/suspension of the clinical trial for safety reasons, a rapid recall of the trial product(s) will be initiated. The investigator or designee must immediately instruct all subjects to stop the clinical trial treatment regimen and return the investigational products to the clinical trial site.

As a general procedure, *GALDERMA R&D* will provide the investigator with a detailed list of units being recalled so that any of the units remaining on site can be put immediately into quarantine.

6.3.6. Dose modification

Local cutaneous reactions including erythema, scaling, dryness, and stinging/burning may be experienced with use of Adapalene 0.3% - BPO 2.5%. All these adverse reactions are easily managed depending upon the severity of these adverse reactions.

Subjects should be instructed to use a moisturizer (the provided one for this trial) and if needed, investigators may reduce temporarily the frequency of the application of Adapalene 0.3% - BPO 2.5% (eg. every other day), or temporarily discontinue use.

These are most likely to occur during the first four weeks of treatment but are mostly mild to moderate in intensity, and usually improve with continued use of the medication. All dose modifications should be documented in the subject's source data and reported in the eCRF (treatment compliance page).

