5. INVESTIGATIONAL PLAN

5.1. OVERALL CLINICAL TRIAL DESIGN

This clinical trial will be conducted as a multi-centre, open-label prospective trial involving subjects aged at least 12 years old inclusive with dark skin type phototype IV to VI from one of the 3 ethnic/race backgrounds: Asian, Latin American and Black/African-American with moderate to severe acne vulgaris on the face and meeting other specific eligibility criteria.

Approximately 60 subjects will be enrolled in 4 sites located in Mauritius, USA and Singapore. 20 subjects are planned from each site.

One third of subjects should have dark skin with **Asian** ethnic/race background:

One third of subjects should have dark skin with **Latin American** ethnic/race background:

One third of subjects should have dark skin with **Black/African-American** ethnic/race background:

In each ethnic/race backgrounds (Asian, Latin American and Black/African-American) approximately **one third** of subjects should have “Severe acne” (IGA 4) and **two third** “Moderate acne” severity (IGA 3).

All eligible subjects will receive Adapalene 0.3% - BPO 2.5% gel (Epiduo[®] Forte / TactuPump[™] Forte gel) once daily on the whole face.

There will be 5 trial visits: at baseline, week 2 (\pm 1 day), week 8 (\pm 3 days), week 12 (\pm 3 days), and week 16 (\pm 5 days).

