7.3.2. Local tolerance assessment

Local cutaneous signs and symptoms (erythema, scaling, dryness and/or stinging/ burning) are possible during treatment with Adapalene 0.3% - BPO 2.5%.

The investigator will evaluate erythema, scaling, dryness and/or stinging/burning at each visit. The investigator will record stinging/burning after discussion with the subject regarding the previous application days. The investigator will ask an open-ended question, taking care not to influence the subject's answer, such as: "Have you experienced any sensations immediately following product application (within 5 minutes)?"

Erythema, scaling, dryness will be evaluated by the investigator, and stinging/burning will be recorded by the investigator after discussion with the subject. The four signs and symptoms will be graded at each follow up visit as follows:

Erythema – abnormal redness of the skin		
None	0	No erythema
Mild	1	Slight pinkness present
Moderate	2	Definite redness, easily recognized
Severe	3	Intense redness
Scaling – abnormal shedding of the stratum corneum		
None	0	No scaling
Mild	1	Barely perceptible shedding, noticeable only on light scratching or rubbing
Moderate	2	Obvious but not profuse shedding
Severe	3	Heavy scale production
Dryness – brittle and/or tight sensation		
None	0	No dryness
Mild	1	Slight but definite roughness
Moderate	2	Moderate roughness
Severe	3	Marked roughness
Stinging/Burning – pricking pain sensation immediately after dosing (within 5 minutes)		
None	0	No stinging/burning
Mild	1	Slight warm, tingling/stinging sensation; not really bothersome
Moderate	2	Definite warm, tingling/stinging sensation that is somewhat bothersome
Severe	3	Hot, tingling/stinging sensation that has caused definite discomfort

Note: *Stinging/Burning should NOT be assessed at the baseline visit*

An Adverse Event will be recorded if the severity of the signs and symptoms is such that:

- The subject's participation in the trial is interrupted at his/her request or at the investigator's request **after the first four weeks** of treatment.
- The subject permanently discontinues the treatment at his/her request or at the investigator's request.
- The subject requires concomitant prescription or OTC therapy (other than moisturizers).

Note: *Need for increased moisturizer use does NOT constitute an AE.*

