9.1.1. Variables to be statistically analyzed

The following variables will be analyzed:

Subject reported outcome variable

- *DLQI/cDLQI at Baseline, Week 12 and last visit*
- *Subject satisfaction questionnaire at Week 12 and last visit*

Efficacy variables

- *IGA score: % of subjects across scores at each visit*
- *GAI score: % of subjects across scores at Week 12 and last visit*

Safety variables on safety population

- *PIH: Raw value at each visit and % change from baseline at each post-baseline visit*
- *Local tolerance: Raw value at each visit and worst-score across visit, % of Subjects across scores at each post-baseline visit*
- *Incidence of adverse events*
- *Incidence of serious adverse events*

Other variables

- *Cosmetic acceptability questionnaire at last visit*

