9.1.4. Statistical analyses

No inferential statistics will be performed. All variables will be descriptively summarized on ITT population and on APT population for the safety variables. The last observation carried forward (LOCF) method will be used to impute missing efficacy values.

Any changes of the statistical analyses decided after the database lock will be justified and documented.

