9.2. SAMPLE SIZE DETERMINATION

As no inferential statistics will be performed, no statistical rationale of sample size can be used. However, a total of 60 subjects to evaluate the subject reported outcomes (quality of life and satisfaction survey), can be considered as sufficient.

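### No tolerance grade is required when the gel is reduced or paused between visits, so the worst score for erythema, scaling and dryness can miss the reaction that led to the change

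*Combined protocol and SAP*

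**What the plan says.** **Dose modification (6.3.6).** For local reactions the investigator may temporarily lower the application frequency or stop the gel. The section does not tie this to a visit. The record required is: "All dose modifications should be documented in the subject's source data and reported in the eCRF (treatment compliance page". The same section expects these reactions mostly in the first four weeks.

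**Grading (7.3.2).** "The investigator will evaluate erythema, scaling, dryness and/or stinging/burning at each visit"; and again, "The four signs and symptoms will be graded at each follow up visit as follows". By 5.1 and the flow chart in 5.4, the follow-up visits are Weeks 2, 8, 12 and 16. Sections 4.5.6 and 5.5.6 add the next visit's procedures at early termination. Stinging/burning is recorded after asking about earlier applications. Erythema, scaling and dryness have no such look-back.

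**Adverse events (7.3.2 and 8.1.1).** The expected signs become adverse events only on interruption after the first four weeks, permanent discontinuation, or a need for added therapy other than moisturizer.

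**Analysis (9.1.1 and 9.1.2.3).** Local tolerance is summarised as "Raw value at each visit and worst-score across visit", plus the distribution of scores at each post-baseline visit. Missing tolerance values are not imputed.

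**The concern.** A worst score is read as the peak irritation that a subject had. Suppose a reaction between two visits leads the investigator to cut back or pause the gel. By the next grading day the subject has had less gel or none, and the skin may have settled. The lower grade then enters the worst score, and no other grade was required.

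The loss is unlikely to be random. More severe reactions are more likely to prompt a modification, so the higher grades are the ones at risk. Tolerability is part of the hypothesis in 3.2, and section 2.1 describes these subjects as sensitive to topical retinoids. The trial has one arm, so there is no comparator in which the same under-capture would occur and offset it.

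The adverse event rules do not close the gap. A reduction in frequency at any time, or a pause in weeks 1 to 4, managed with the supplied moisturizer, need not produce an adverse event. Those are also the weeks in which 6.3.6 expects most reactions.

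**Working it through.** The plan states no figure to reproduce here: section 9.1.4 says "No inferential statistics will be performed" and section 9.2 gives no statistical basis for the 60 subjects. The check has three steps.

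**1. Where each kind of modification leaves a trace**

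| Situation | 7.3.2 grade at that time | Adverse event by itself |
|---|---|---|
| Change decided at a scheduled visit | Yes, same-visit grading | Depends on the rules below |
| Frequency reduced between visits, any time | Not required | No |
| Pause between visits, weeks 1–4 | Not required | No |
| Interruption between visits, after week 4 | Not required | Yes |
| Permanent discontinuation | Yes, where the early termination visit takes place | Yes |
| Added therapy other than moisturizer | Not required between visits | Yes |

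Rows two and three are the gap: neither a grade nor an adverse event is required. In rows four and six the reaction reaches the adverse event tables but not the worst score.

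**2. How far apart the gradings are**

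Inputs are the nominal days and windows in 5.1: day 14 (±1), 56 (±3), 84 (±3) and 112 (±5). The gap is the later day minus the earlier day; the range comes from the windows.

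- Baseline to Week 2: 14 days (13 to 15)
- Week 2 to Week 8: 56 − 14 = 42 days (38 to 46)
- Week 8 to Week 12: 84 − 56 = 28 days (22 to 34)
- Week 12 to Week 16: 112 − 84 = 28 days (20 to 36)

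Only one post-baseline grading falls in the first 28 days, and the next comes about six weeks later.

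**3. Illustration of what the spacing can miss**

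Assumptions, none of them from the documents: an episode is visible for L consecutive days, and its onset is equally likely on each day of a stated range. The share overlapping a grading day is the number of onset days for which a grading falls between onset and onset + L − 1, divided by the number of possible onset days. For L up to 14, only day 14 can be hit, and L onset days hit it.

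| L | Onset on days 1–28 | Onset on days 1–14 |
|---|---|---|
| 3 days | 3/28 = 11% | 3/14 = 21% |
| 7 days | 7/28 = 25% | 7/14 = 50% |
| 14 days | 14/28 = 50% | 14/14 = 100% |

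The second column is there because 2.3.2 says reactions usually come early and then lessen. Dose modification does not enter either column. The table shows how sparse the gradings are, not how much the worst score is biased by reducing or pausing the gel.

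**The case against.** Four stronger readings are tempting, and the documents support none of them.

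- A reader might infer that the worst score is generally taken after the gel has been cut back. The only investigator contacts that the protocol schedules are the visits and early termination, and a decision made there is graded the same day. The gap concerns unscheduled contacts, whose frequency is unknown.
- A reader might take the complements in the first column, 50% to 89%, as the share of reactions lost through dose modification. They would be the same if no dose were ever changed, and they depend strongly on the assumed onset.
- A reader might say that the worst score is the only per-subject summary of peak irritation. Section 9.1.3 also tabulates subjects by highest adverse event intensity, and the satisfaction questionnaire asks how bothersome side effects were. Both are partial, but they exist.
- A reader might say that the grade goes unrecorded. Section 6.3.6 also requires source documentation, which may contain a description. What is missing is a requirement to grade on the 7.3.2 scales and bring the grade into the analysis.

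It is also fair to say that a visit-based worst score is a common convention, that 9.1.1 labels it as such, and that the trial is descriptive with subject-reported outcomes as its main objective. Telephone contact cannot give an investigator's grade of erythema or scaling. These points limit the weight of the concern. They do not supply a grade for a modification between visits.

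**Conclusion.** The concern holds in a limited form. For reductions or pauses between visits, the worst score for erythema, scaling and dryness can miss the reaction that was acted on. When the change is a frequency reduction, or a pause in the first four weeks, the adverse event tables need not show it either. The direction is towards a more favourable tolerability result, on the reasonable assumption that more severe reactions are more often acted on.

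The size cannot be derived: the documents give no episode length, onset pattern, reaction rate or frequency of unscheduled contacts. This is a worthwhile low-cost improvement. It does not undermine the main objective. It has to be made at data collection, because the separate SAP foreseen in 9.1 can redefine the variable but cannot supply grades that nobody recorded.

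**What to change.** **Section 6.3.6 (data collection only).** When the subject is seen at an unscheduled contact at which the gel is reduced or paused for a local reaction, record the date and the four 7.3.2 grades with the modification on the eCRF compliance page. If the contact is by telephone, record stinging/burning only and flag it as a telephone grade.

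**Section 9.1.1.** Report the worst score over all post-baseline grades (scheduled, early termination and at dose modification) beside the worst score over scheduled visits. Keep the by-visit tables on scheduled visits.

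**Cost.** Four grade fields, a date and a telephone flag on a page already completed for each modification, and one added line in section 9. No visit is added, and the rule for modifying the dose is unchanged. The downside is that subjects with modifications have more gradings and so more chances of a high worst score; showing both versions makes that visible. Modifications arranged by telephone will still lack grades for erythema, scaling and dryness, and the report should say so.
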